## 5.5. Required data

Demographic details	
Age	Year of birth
Sex	Male/ Female/ Other
Ethnicity	European/ Pasifika/ Maori/ Asian/ Middle-Eastern/ Latin American/ African (MELAA)/ other ethnicity
Postcode	
Weight	kg
Height	cm
Smoking history	Current smoker /previous smoker /never smoker e-cigarette /cigarette
Admission details	
Date of first review by doctor/prescriber	Date (dd/mm/yyyy)  *From ED admission note
Time of first review by doctor/prescriber – as per admission note	24 hour clock time
Pancreatic enzymes at admission	Lipase/ Amylase/ Pancreatic amylase (tick one or more and give admission level and indicate what 3x upper limit is
Lipase/ amylase/ pancreatic amylase level	U/L
Epigastric pain confirmed on admission note	Yes/Non-epigastric abdominal pain/ No abdominal pain
Confirmation of AP diagnosis with imaging as per radiological report	MRI/ CT/ Abdominal USS
Charlson Comorbidity Index ( Appendix E )	Score out of 37
Aetiology	
Significant ETOH history investigated in first 72 hours	Yes - from medical history, Yes - ETOH blood test, No

Hypertriglyceridemia investigated in first 72 hours	Yes/No
Acute pancreatitis severity	
Predicted severity on admission as documented in clinical notes (72 hours)	Mild/ moderately severe/ severe
Method used to predict severity	Modified Glasgow/ Ransons'/ BISAP/ APACHE II/ SIRS/ CRP (>150)/ Other (please specify)/ Clinical judgement (no prediction tool)/ No prediction made.
Imaging	
CT assessment performed in the first 72 hours of presentation	Yes/ No
Indication for CT prior to 72 hours	Diagnostic uncertainty/ confirmation of severity based on clinical predictors of severe AP/ Failure to respond to conservative treatment or in the setting of clinical deterioration/ other (please specify)
Imaging of the gallbladder during admission	USS/ CT (gallstones seen on CT)/ MRI/ EUS/ prior imaging confirming gallstones/ previous cholecystectomy/ no imaging
Antibiotics	
Antibiotics administered in first 72 hours of presentation	Yes/ No
Indication for antibiotics	Cholangitis concomitant extrapancreatic infection/ prophylactic/ other – please state
Analgesia	
Simple analgesia (paracetamol/ NSAIDs) prescribed	Paracetamol/ NSAIDs/ Not charted
Simple analgesia frequency	regular/ PRN
Date simple analgesia first administered	Date (dd/mm/yyyy)
Type of opioid prescribed (if any)	Codeine/ Morphine/ Fentanyl/ Tramadol/ Oxycodone/ Other (please specify)/ no opioids prescribed
Date opioid analgesia first administered	Date (dd/mm/yyyy)
Time opioid medication is administered to patient	24 hour clock
Route	PO/ IV
(If regular) daily dose	mg
(If PRN) total dose in first 72 hours	mg

(If yes) Date opioids first administered	Date (dd/mm/yyyy)
(If yes) Time opioid medication first administered as per drug chart?	24 hour clock
Further analgesic modalities	PCA/ ketamine/ local nerve blocks/ other (please specify)
Transfer to different hospital	
Patients with predicted severe disease discussed with specialised pancreas service ( Appendix B ) in first 72 hours from admission	Yes/ No/ not applicable
Patient transferred to a different hospital in the first 72 hours?	Yes/No
(If yes) Date of transfer	Yes/No
(If yes) Location transferred to	List of hospitals
(If yes) Reason for transfer to different hospital?	Severe disease/ requires ERCP/ requires interventional management of local complication/ other (free text)
ERCP	
Cholangitis in first 72 hours ( Appendix F )	Yes/ No
Cholestasis in first 72 hours (radiological + deranged LFTs)	Yes/ No
ERCP performed in the first 72 hours	Yes/ No
Fluid management*	
Baseline variables	
Bag 1	
Date of administration	Date (dd/mm/yyyy)
Time of administration	Time (24-hour)
Volume administered	Volume (ml)
How long does fluid run for?	Time (hours)
Type of fluid	0.9% Normal saline/ Hartmann's/ plasmalyte/ colloid/ 0.45 saline + dextrose/ 0.18 saline + dextrose/ other (please specify)
Further administration of intravenous fluid (IVF) in the first 3 days of admission? ( Appendix B )	Yes/no
Bag 2	
Date of administration	Date (dd/mm/yyyy)
Time of administration	Time (24-hour)

Volume administered	Volume (ml)
Time fluid is administered	Time (hours)
Type of fluid	0.9% Normal saline/ Hartmann's/ plasmalyte/ colloid/ other (please specify)
Further administration of intravenous fluid (IVF) in the first 2 days of admission?	Yes/no
Documented fluid review after 12 hours ( $\pm$ 4 hours)	Yes/no
Documented fluid review after 24 hours ( $\pm$ 4 hours)	Yes/no
Documented fluid review after 48 hours ( $\pm$ 4 hours)	Yes/no
Documented fluid review after 72 hours ( $\pm$ 4 hours)	Yes/no
Early Nutritional support	
On admission patient kept nil by mouth (NBM)	Yes/no
Indication for NBM	for ultrasound scan/ for surgery/ for ERCP/ unknown reason/ other (please specify)
Patient tolerating PO oral intake (clear fluids) by 24 hours	Yes/no
Patient tolerating PO oral intake (clear fluids) by 48 hours	Yes/no
Patient tolerating PO oral intake (clear fluids) by 72 hours	Yes/no
Enteral feeding started in the first 72 hours?	Yes/no
Tolerating enteral feed	Yes/no
Type of Enteral feeding	NJ/NG
Rate of enteral feed	ml/hr
PN in the first 72 hours?	Yes/no
Rate of PN	ml/hr
Anticoagulation	
On regular anticoagulation therapy prior to admission	Warfarin/ dabigatran/ rivaroxaban/ other (please specify)/ Not on regular anticoagulation therapy
Regular anticoagulation continued on admission	Yes/No
(If yes) type of anticoagulation drug	warfarin/ dabigatran/ rivaroxaban/ other
Regular anticoagulation commenced on	Yes - at 24 hours/ Yes - at 48 hours/ No

admission	
Anticoagulation commenced on admission	Prophylactic-dose clexane/ treatment-dose clexane/ anticoagulation not started/ other (please specify)
Local complications in the days prior to the 30-day follow-up	
Necrotising pancreatitis ( Appendix B )	Yes/no
Acute necrotic collections (ANC)	Yes/no
Infected ANC	Yes/no
(If yes) intervention	Endoscopic/ percutaneous/ open necrosectomy
(if yes) date of intervention	Date (dd/mm/yyyy)
Acute pancreatic fluid collection (APFC)	Yes/no
Infected APFC	Yes/no
(if yes) intervention	Endoscopic/ percutaneous/ open necrosectomy
(if yes) date of intervention	Date (dd/mm/yyyy)
Portal/ splenic vein thrombosis	Yes/no
Other local complications	Pleuro-peritoneal fistula/ pleural effusion/ enteric fistula/ gastrointestinal bleeding/ pancreatic ascites/ arterial pseudoaneurysm/ other (free text)
Organ failure and other outcomes during the last 30-days follow-up	
Final aetiology	Alcoholic/ gallstone/ hypertriglyceridaemia/ others
Acute renal failure (as per RIFLE criteria - Appendix A )	Yes/no
Acute renal failure > 48 hours	Yes/no
ICU admission	Yes/no
(If yes) duration of ICU admission	day(s)
New renal dialysis required	Yes/no
(If yes) duration of dialysis	day(s)
New high-flow oxygen/ AIRVO requirement	Yes/no
Duration of high-flow/ AIRVO	days
Noninvasive ventilation required	Yes/no
(If yes) duration of noninvasive ventilation	days
Mechanical ventilation required	Yes/no

(If yes) duration of mechanical ventilation	day(s)
Inotropes required	Yes/no
(If yes) duration of inotropic support	day(s)
Date of mortality (within 30 days of first admission)	Date (dd/mm/yyyy)/ not dead
Date of discharge	Date (dd/mm/yyyy)/ not discharged

*\* Fluid therapy data collection guide: If collaborators respond, 'yes' to the question 'further administration of IVF in first 72 hours of admission?' a further set of questions will arise for 'bag 2', 'bag 3' etc.*

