### Secondary Aims:

- To measure the variation in compliance with QPIs between each hospital in AoNZ for each management domain for the management of AP during the first 72 hours after admission.
- To correlate compliance (overall and for each management domain) with QPIs and defined clinical outcomes stratified by AP severity.
- To compare clinical outcomes between compliant and non-compliant management of patients stratified by AP severity.

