## 3. Quality Performance Indicators

Multiple practice guidelines have been published for the management of AP (14–19). The recommendations in these guidelines are usually based on a systematic review of the relevant literature and the evidence on which is based on the available evidence, which is usually graded. Quality performance indicators will be drawn from these evidence-based recommendations for each of the nominated management domains that are relevant to the management of patients within the first 72 hours from admission to hospital. Any differences in the recommendations between the source guidelines will be resolved by discussion amongst the Scientific Advisory Group and consensus established for the QPIs.

The QPIs were developed for the following management domains: (Appendix D: Table 1 with guidelines)

**Table 1.** Quality Performance Indicators

	Domain	QPI	Ref*	Metrics
1	Diagnosis	All patients diagnosed within 12 hours of admission	IAP	RAC criteria for diagnosis: enzymes 3xUL, typical pain ± CT scan
2	Aetiology	All patients had tests for aetiology determined within 24 hours of admission	IAP	U/S for gallstones ETOH history with intake (units per week, timing of binge to pain) If both negative then lipids, IgG4, drugs
3	Severity (predicted)	All patients had prediction of severity on admission	IAP	N / Y, if yes method (drop-down of all options and other) Further drop-down bar will the give options for severity (mild, moderate, and severe)

4	Severity (actual)	All patients had actual severity determined at 48 hours	-	N / Y, if yes method (drop-down RAC, DBC and other) Further drop-down bar will the give options for severity (mild, moderate, and severe)
5	CT scan	Initial CT assessment performed after 72-96 hours if poor response to initial management or clinical deterioration, unless there is diagnostic uncertainty. Not required for severity prediction.	IAP	N / Y, if yes indication (drop-down with other)
6	Transfer	All patients with predicted or actual severe AP in the first 72 hours are discussed with specialist pancreas service.	Nice	N / Y Indication for transfer (drop-down)
7	Analgesia	All patients given narcotic analgesia within one hour of admission	-	Step-up or step-down approach? IV analgesia given on admission N / Y NSAIDS given to mild AP Analgesics prescribed

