## 8. Statistical analysis

The study will be reported in accordance with the Strengthening the Reporting of Observational Studies in Epidemiology (STROBE) statement (21). The primary analyses will be descriptive assessments of adherence to unambiguous recommendation in the selected domains of early AP management. Descriptive analysis will be performed where normal continuous variables will be compared via student's t test, and non-normal continuous variables will be compared via Mann-Whitney U test; if >2 categories a one-way ANOVA or Kruskal-Wallis test will be used for normal and non-normal variables respectively, Chi-square tests will be used to detect differences between categorical variables. All analyses will be conducted under a two-tailed hypothesis. Multiple imputation may be used in the case of missing data.

Secondary analyses will evaluate the differences in results according to the hospital. Risk-adjusted funnel plots will be produced to test the performance of individual, anonymised centres for normal rates of primary and selected secondary outcomes. Funnel plots' Y-axes will demonstrate QPI of a management domain and X-axis will show the number of patients admitted in each hospital. Furthermore, differences in clinical outcomes between patients that are managed according to best available evidence (QPI) and those that were not will be explored through mixed effects multivariable logistic models. These models will use the patient at the fixed effect level 1 and the hospital as the random effect level 2 (using the R lmer package) will be performed. A one level, fixed effect binary logistic regression model using a pooled dataset from 5 multiply imputed datasets will also be used in the event of substantial missing data.

Variable selection will be based on statistically significant univariable analysis and those variables deemed clinically significant. Fixed, forced entry will be used to adjust the main outcome measure, The effect of interaction, and sequential removal of non-significant variables will be assessed using changes in Akaike information criteria for multilevel models, and p-values for multiple imputed fixed models.

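### With no admission physiology in the Required data list, the secondary compliance-outcome comparisons are open to substantial residual confounding by severity on arrival

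*Protocol*

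**What the plan says.** The Secondary Aims (Section 2) include one "To compare clinical outcomes between compliant and non-compliant management of patients stratified by AP severity". Section 8 carries this into analysis: "differences in clinical outcomes between patients that are managed according to best available evidence (QPI) and those that were not will be explored", using mixed-effects logistic models with hospital as a random effect. No severity covariate is named. On adjusters, Section 8 says "Variable selection will be based on statistically significant univariable analysis and those variables deemed clinically significant". It also states "Risk-adjusted funnel plots will be produced to test the performance of individual, anonymised centres".

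Section 5.5 lists what is collected. The items that could describe the patient at or near arrival are:

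- demographics, weight, height, smoking and the Charlson index;
- pancreatic enzyme level, the only laboratory value;
- alcohol and triglycerides, recorded only as investigated or not, and final aetiology, recorded at follow-up;
- cholangitis and cholestasis, as yes/no flags over the first 72 hours;
- predicted severity in three levels, as documented in the notes within 72 hours, and the method used, whose last options are "Clinical judgement (no prediction tool)/ No prediction made".

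QPI 3 in Table 1 reads "All patients had prediction of severity on admission".

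**The concern.** How ill a patient is on arrival plausibly affects both the speed and completeness of early care and the risk of organ support, intervention or death. If it is not measured, a difference in outcome between compliant and non-compliant patients may reflect who was sicker, and the direction is not known in advance. Faster care for sicker patients would make non-compliance look protective; harder-to-deliver care in sicker patients would make it look harmful.

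This matters because Section 1 expects the study to show excess morbidity linked to non-compliance. An analysis plan cannot repair the gap later, since it cannot adjust for values that were never recorded.

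**Working it through.** The protocol gives no figure to reproduce here. The check has three parts.

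**1. Fields in Section 5.5 against what adjustment needs.** The list has no heart rate, blood pressure, temperature, respiratory rate, oxygenation, creatinine, urea, haematocrit, white cell count or CRP value. An oxygenation ratio is used as an exclusion threshold in Section 5.4 but is not recorded. The severity category may come from a named score, but neither the score nor its components is kept. There is no time field, so a prediction written on day three is stored like one made at the door.

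**2. Overlap for QPI 3.** As the form codes it, a patient with no prediction fails QPI 3 and has no severity category, while a patient with a prediction passes and has one. When QPI 3 is the exposure:

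- every stratum of predicted severity contains only compliant patients, and the no-prediction stratum contains only non-compliant ones, so no stratum allows a comparison;
- a complete-case model drops every failure;
- imputation would have to supply severity for all non-compliant patients from a model fitted to compliant ones, with no physiology to inform it.

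The same patients carry the same gap into any composite that includes QPI 3.

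**3. Illustrations with a true odds ratio of 1.00.**

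*Unadjusted.* Inputs: 20% high-risk on arrival (an assumption; Section 1 gives 20% as the share who develop moderate or severe disease); outcome risk 25% in high-risk and 2% in low-risk patients (assumed); compliance gradients (assumed).

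For compliance of 60% in low-risk and 40% in high-risk patients:

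- Non-compliant: 0.80 × 0.40 = 0.32 low-risk and 0.20 × 0.60 = 0.12 high-risk, total 0.44. Events 0.32 × 0.02 + 0.12 × 0.25 = 0.0364. Risk 0.0364 / 0.44 = 8.27%.
- Compliant: 0.48 low-risk and 0.08 high-risk, total 0.56. Events 0.0096 + 0.0200 = 0.0296. Risk 5.29%.
- Odds ratio, non-compliant against compliant: (0.0364 / 0.4036) / (0.0296 / 0.5304) = 1.62.

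| Compliance, low-risk / high-risk | Risk, non-compliant | Risk, compliant | Odds ratio |
|---|---|---|---|
| 60% / 40% | 8.27% | 5.29% | 1.62 |
| 40% / 60% | 5.29% | 8.27% | 0.62 |
| 60% / 50% | 7.48% | 5.97% | 1.27 |
| 50% / 60% | 5.83% | 7.31% | 0.79 |

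*Adjusted for the documented category (a domain other than QPI 3).* Inputs: 20% high severity; outcome risk 20% or 40% in that group (Section 1 gives 20-40% as mortality in severe disease only) and 2% otherwise (assumed); compliance 60% in low and 30% or 45% in high severity (assumed); prediction sensitivity/specificity 0.7/0.8 or 0.9/0.9 (assumed); documentation at random in 30% to 100% of patients (assumed). The summary is the Mantel-Haenszel odds ratio, Σ(ad/n) / Σ(bc/n), from expected cell proportions, where a and b are non-compliant patients with and without the event, and c and d are compliant patients with and without it.

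One case in full: high-severity risk 20%, compliance 60% / 30%, sensitivity and specificity 0.9, all documented.

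- Predicted high (n = 0.26): a = 0.02584, b = 0.13216, c = 0.01176, d = 0.09024; ad/n = 0.00897, bc/n = 0.00598.
- Predicted low (n = 0.74): a = 0.00856, b = 0.29344, c = 0.00984, d = 0.42816; ad/n = 0.00495, bc/n = 0.00390.
- Odds ratio: (0.00897 + 0.00495) / (0.00598 + 0.00390) = 1.41, against 1.94 crude.

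Across all settings:

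| Analysis | Odds ratio |
|---|---|
| Crude | 1.39 to 2.37 |
| Adjusted, with a no-prediction level, 30-70% documented | 1.24 to 2.28 |
| Adjusted, complete cases | 1.18 to 2.10 |
| Adjusted, 100% documented | 1.18 to 2.10 |

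Adjustment for the documented category reduces the bias and does not remove it. This set covers only gradients in which sicker patients are less often compliant.

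**The case against.** The strongest reply is that the Secondary Aims already stratify by severity. Appendix A defines actual severity, Table 1 lists its capture at 48 hours (QPI 4), and Section 5.5 collects organ failure and local complications to 30 days. The stratification is indeed planned, but it does not answer the point. Appendix A severity rests on organ failure and its persistence beyond 48 hours, and on local complications. These emerge after early care has begun and overlap with ventilation, renal replacement, inotropes and intervention for complications, which are the outcomes compared. The QPI 4 item also has no field in Section 5.5.

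Other objections stand and limit the point:

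- A reader might infer that the models cannot adjust for severity at all. The documents do not support that. Age, comorbidity, aetiology and the documented category allow partial adjustment, and the cholangitis criteria in Appendix F include fever, white cells and CRP.
- A reader might take 1.62 or 0.62 as the bias in the planned models. They are crude values on assumed risks and gradients, and nothing in the protocol fixes a direction.
- A reader might extend the loss of overlap to every domain. It holds for QPI 3 and for the patients it affects in composites. It also assumes that QPI 3 failure means no prediction made; the protocol does not say how clinical judgement alone is scored.
- A reader might conclude that hospitals' outcome funnel plots will be wrongly labelled as risk-adjusted. Section 8 mentions selected secondary outcomes but puts the QPI of a domain on the vertical axis, and QPI variation is itself a secondary outcome. Clinical-outcome funnel plots are not clearly planned.
- The final REDCap form is not shown, so the check covers the Required data list only.

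**Conclusion.** The point holds as residual confounding in a secondary aim. The listed data give no measure of acute illness on arrival that is recorded for every patient independently of clinicians' documentation. For QPI 3, failures coded as having no prediction cannot be adjusted for or stratified by predicted severity.

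The size is unknown. The illustrations show only that a null effect could plausibly appear as a moderate association in either direction before adjustment, and that under the second set of assumptions 1.18 to 2.10 remains even with complete documentation. All of this depends on assumed outcome risks, compliance gradients and prediction accuracy. The primary outcome, a descriptive proportion managed in compliance, needs no such adjustment and is unaffected. The change is worth making because it is cheap and the missing values cannot be supplied by analysis.

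**What to change.** - **Section 5.5:** add the first recorded admission values needed to compute one score the form already lists, for example SIRS or BISAP.
- **Section 8:** state that the score is computed centrally for every patient with sufficient data and is forced into the compliance-outcome models, and into any risk-adjusted funnel plot of a clinical outcome if one is produced.
- **Section 2:** name this score, not Appendix A severity, as the baseline stratifier for these comparisons.
- **QPI 3:** use the documented prediction only to score this indicator.

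The cost is about six to eight extra chart-abstracted fields per patient and a short addition to Section 8. No extra tests or patient contact are needed. The downside is a little more data entry and some missing values. If collection has already closed, the retained key linking REDCap and hospital numbers makes later abstraction technically possible, subject to approvals.

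If the fields are not added, report the compliance-outcome results as descriptive associations not adjusted for severity on arrival.

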**Appendix A (i) - Revised Atlanta Classification of AP severity**

Severity	Definition
Mild acute pancreatitis	Absence of organ failure Absence of local complications
Moderately severe acute pancreatitis	1. Local complications AND/OR 2. Transient organ failure (<48 hours)
Severe acute pancreatitis	1. Persistent organ failure (>48 hours)

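### The only field recording specialist discussion covers predicted severe AP, so QPI 6 is measured on part of its stated population (predicted or actual severe), with bias of unknown size and direction

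*Protocol*

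**What the plan says.** Protocol section 3, Table 1, row 6 (Transfer) states the indicator as "All patients with predicted or actual severe AP in the first 72 hours are discussed with specialist pancreas service". Its metric is a yes/no entry plus the indication for transfer, with no restriction to predicted severity.

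Protocol section 5.5, in the block on transfer to a different hospital, collects the discussion in a single field, "Patients with predicted severe disease discussed with specialised pancreas service", limited to the first 72 hours from admission. The answers are "Yes/ No/ not applicable".

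Section 5.5 also records predicted severity as documented in the notes, and the method of prediction. The last two options for method are "Clinical judgement (no prediction tool)/ No prediction made". Actual severity is the subject of a separate indicator, QPI 4: "All patients had actual severity determined at 48 hours". Appendix A (i) defines severe AP by organ failure persisting beyond 48 hours.

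**The concern.** The indicator has two limbs, predicted severe and actually severe, and the form asks about one. For a patient who is severe within 72 hours but has no severe prediction on record, the literal entry is *not applicable*, whether or not the specialist service was contacted. That patient can neither pass nor fail QPI 6.

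QPI 6 contributes to overall compliance, the primary outcome (section 4.1). It also contributes to the between-hospital comparison by domain (section 4.2), which section 8 displays in funnel plots, and to the planned comparison of outcomes by compliance within severity strata (section 2). An analysis plan cannot restore an answer that was never recorded. Section 5.3 has the local copy of the data destroyed after upload, so later repair would mean re-identifying patients through the retained key and reviewing charts again.

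**Working it through.** The protocol gives no expected adherence for QPI 6, so there is no figure to reproduce. The check compares the texts and then illustrates the possible error.

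**1. Populations.** Table 1, row 6: predicted severe *or* actually severe. Section 5.5 field: predicted severe. The difference is the group that is actually severe within 72 hours without a severe prediction, including those for whom no prediction was made.

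**2. Can another field in section 5.5 recover this group?**
- Predicted severity is the only severity-grade field. QPI 4 has no matching item.
- Organ-failure items are 30-day yes/no and duration entries without onset dates, so severity reached within 72 hours cannot be rebuilt reliably.
- Severe disease appears as a reason for transfer, but only for transferred patients, and QPI 6 concerns discussion, not transfer.

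None of these records the discussion for the omitted group.

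**3. Effect between hospitals.** A hospital that seldom documents predictions has fewer patients scored on QPI 6. Poor performance on QPI 3 (severity prediction) thus removes patients from QPI 6, whichever group is discussed more often.

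**4. Timing.** Severe AP needs more than 48 hours of organ failure. If it must be reached within 72 hours of admission, the failure has to begin within about 72 − 48 = 24 hours of admission. This limits the size of the omitted group. Section 5.3 also puts the first data collection at or before 48 hours, when failure that began after admission cannot yet have lasted more than 48 hours.

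**5. Illustration (all values assumed).** Let P be the number predicted severe, whether or not they become severe, and U the number actually severe without a severe prediction. Then u = U/(P + U). With adherence a1 in the first group and a2 in the second:
- the form reports a1;
- the Table 1 rate is (1 − u)·a1 + u·a2;
- the error is u·(a1 − a2).

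Each cell gives form rate, Table 1 rate and error in percentage points.

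| u | a1 = 0.80, a2 = 0.50 | a1 = a2 = 0.70 | a1 = 0.50, a2 = 0.80 |
|---|---|---|---|
| 0.10 | 80.0, 77.0, +3.0 | 70.0, 70.0, 0 | 50.0, 53.0, −3.0 |
| 0.25 | 80.0, 72.5, +7.5 | 70.0, 70.0, 0 | 50.0, 57.5, −7.5 |
| 0.40 | 80.0, 68.0, +12.0 | 70.0, 70.0, 0 | 50.0, 62.0, −12.0 |

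The size depends on u and on the adherence gap, and the sign on which group is discussed more often. The protocol supplies none of these.

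**The case against.** The strongest reply is that the gap is narrow and partly covered. The prediction field accepts documentation up to 72 hours and allows clinical judgement as a method, so a patient who deteriorates early may be written up as severe in time and be scored. Severe AP within 72 hours needs early organ failure, so few patients may be lost. *Not applicable* is not defined and could also serve patients already under a specialised service, so a collector might answer yes or no regardless. QPI 6 is one of twelve indicators. These points stand as limits on size. They do not make the field's population the same as the indicator's.

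A reader might infer that the form flatters hospitals by scoring only an easier group. The documents do not support that. Nothing in them says which group is discussed more often, and established organ failure could prompt a call more readily than a risk score does.

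A reader might also assume that 30% to 60% of actually severe patients are unpredicted, apply that share to the whole QPI 6 population, and get a Table 1 rate of 71% (0.8 × 0.7 + 0.5 × 0.3) down to 62% (0.8 × 0.4 + 0.5 × 0.6) against 80% on the form. That uses the wrong denominator: P also includes predicted-severe patients who never become severe, so u is smaller than the unpredicted share of severe cases. It also ignores the 72-hour limit, and the 80% and 50% are chosen values that fix the direction in advance.

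**Conclusion.** The mismatch is real and should be corrected. Following the form as written, QPI 6 adherence, its hospital comparison and its contribution to the primary outcome are measured on only part of the population set in Table 1. This rests on a literal reading of the field and its not-applicable option. That reading is reasonable, and the protocol offers no other.

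The size and direction of the bias are unknown. Under the assumed values the error in QPI 6 runs from 12 points too low to 12 points too high and vanishes if both groups are discussed equally often. The true share omitted may lie at or below the low end of the assumed range. The effect on the primary outcome cannot be sized, because it also depends on how the indicators are combined into overall compliance. The dependence of the scored denominator on how often a hospital documents predictions holds without any of these assumptions.

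**What to change.** Reconcile Table 1, row 6 with section 5.5.

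- Reword the field so that its population matches the indicator, for example: *AP predicted severe or actually severe: case discussed with a specialised pancreas service within 72 hours? Yes / No / not severe*.
- Add an actual-severity item with the date and time that the grade was reached, completed after the 72-hour window has closed. Rewording alone would leave collectors to judge actual severity with nothing on record to verify the denominator.
- Report QPI 6 separately for predicted-severe patients and for those who were actually severe only.

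If actual severity will not be collected, restate QPI 6 in Table 1 and in reports as measured in predicted-severe patients only.

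The cost is one reworded and one or two added REDCap fields, filled from the chart review already planned. Patient care is not affected. If the form has already been used as it stands, the choice is between restating the indicator and a second chart review through the retained key.
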